Study Protocol

Evaluation of rGH Therapy to Prevent Muscle Atrophy in Patients With ACL Tears

ClinicalTrials.gov Identifier: NCT02420353

Principal Investigator: [name], ATC

University of Michigan Medical School IRB Protocol: HUM00087702

September 24, 2019

Abstract and Hypothesis

Anterior cruciate ligament (ACL) tears are among the most frequent traumatic knee injuries that occur in athletes. Despite advances in minimally invasive surgical reconstruction techniques and aggressive rehabilitation, this atrophy and loss of strength can persist even after patients return to full activity and can place them at considerable risk for re-injury and developing osteoarthritis (OA). The design of new therapeutic interventions to prevent muscle atrophy is needed to advance the care of patients who suffer from ACL injuries. The growth hormone (GH)/insulin-like growth factor-1 (IGF-1) axis plays an important role in promoting muscle growth and protecting muscle from atrophy. While GH therapy has shown promise in protecting immobilized muscle from various models of disuse atrophy, it remains unknown whether GH can help to restore strength and protect against the loss in strength that occurs after ACL tear. Our purpose is to conduct a randomized, double-blind, pilot placebo-controlled study to gain additional insight into the safety and biological effects of GH on muscle size and strength in patients with ACL tears. ***We hypothesize that, compared to placebo treatment, a six week perioperative course of GH treatment will prevent muscle atrophy and weakness in patients undergoing ACL reconstruction, and cause the return of full quadriceps muscle strength by 6 months after surgery.*** If our hypothesis is supported, GH therapy may help to accelerate the safe return to play of patients that suffer ACL tears, and help to prevent the long-term OA and reduction in quality of life that occur after these traumatic knee injuries.

Background and Rationale

Epidemiology of ACL Tears, Muscle Weakness and Development of Osteoarthritis. ACL tears are among the most frequent knee injuries in physically active individuals, with tear rates in the US around 250,000 per year (Griffith 2005). Despite our best efforts in rehabilitation, many patients that suffer from ACL tears and undergo ACL reconstruction (ACL-R) have a persistent atrophy and weakness of their quadriceps muscles. In addition to reducing physical performance and increasing the susceptibility to repeated injuries, several studies have indicated this loss of strength can alter knee kinematics in a way that promotes the development of early-onset osteoarthritis (OA). For example, in a population of female soccer players who suffered ACL tears at an average age of 19 years, 12 years after the injury there was radiographic OA present in 51% of injured knees, while only 7% of uninjured contralateral knees showed signs of OA (Lohmander 2004). In male soccer players who suffered ACL tears, 14 years after the tear 75% of injured knees demonstrated signs of OA, compared to only 4% of uninjured, contralateral knees (von Porat 2004). Surgical reconstruction of torn ACLs, while helpful in restoring some joint kinematics and proprioception, does not appear to modify the likelihood of development of OA in ACL-R patients (Roos 2005).

Many studies have reported persistent weakness quadriceps muscles following ACL-R, typically around 30-40% at 6 months to one year following surgery (Ingersoll 2008). This weakness appears to occur for all types of ACL autografts and allografts. Muscle weakness following ACL tear is associated with the development of OA (Palmieri-Smith 2008, Keays 2010). This weakness likely plays two roles in the development of OA following ACL tear. First, muscle is an important dynamic stabilizer of the knee joint. Strength is required to precisely control the 3D motion of the knee during locomotion, and muscle weakness can lead to the development of pathological mechanics that cause greater wear of articular cartilage (Andriacchi 2004). Second, because muscle can transmit loads across the knee joint and function as a "shock absorber" during eccentric contractions (LaStayo 2003), greater strength allows the muscle to transmit forces throughout the kinetic chain and reduce loads on articular cartilage.

Developing strategies to prevent muscle atrophy following ACL tears will help reduce the rates and severity of knee OA and enhance the physical performance of athletes that undergo ACL-R.

While the vast majority of patients who suffer ACL tears are recreational athletes or "weekend warriors", ACL tears can have a significant negative impact on the playing careers for professional and elite athletes as well. In the NBA, almost a quarter of players who tear their ACLs do not return to playing professional basketball (Busfield 2009). NFL players that suffer ACL tears only have a 63% chance of returning to play, and for those athletes who do return to play in the NFL miss on average 78% of the regular season and require almost 11 calendar months to return to competition (Shah 2010). Improving the recovery of professional athletes with ACL tears will likely have an important short term impact on their playing careers, but also help to avoid long-term osteoarthritis and knee joint weakness that can occur a decade or more after retiring from professional sports.

Molecular Regulation of Muscle Atrophy. At the molecular level, maintaining skeletal muscle mass is a balance between protein synthesis and protein degradation systems. Muscle atrophy can come about due to increased protein degradation or decreased protein synthesis. An overview of these pathways is presented in Figure 1. There are four main pathways that regulate skeletal muscle atrophy, the ubiquitin proteasome, autophagy/lysosome, caspase-apoptotic and calpain systems (reviewed in Sandri 2008 and Gumucio 2013). Myostatin is one of the most well-known atrophy-inducing cytokines, and plays a central role in the activation of all but the calpain proteolytic pathways. The potent effects of myostatin can be readily observed at the whole muscle level, as even small amounts of this cytokine leads to rapid and profound muscle atrophy and reductions in force production (Zimmers 2002, Li 2004, Mendias 2006, Mendias 2011). Since myostatin directs the major proteolytic pathways in skeletal muscle, it is an attractive therapeutic target for the prevention of muscle atrophy. Direct inhibitors of myostatin are currently in development and are likely at least several years away from when they might appear on the market. Employing an indirect way of inhibiting myostatin, though, can be accomplished with existing, approved drugs.

Growth occurs in two parts in skeletal muscle. Muscle fibers are multinucleated cells, and as fibers grow they rely on a pool of resident stem cells, called satellite cells, to provide new nuclei to growing fibers (Hawke 2001). Prolonged periods of muscle disuse can decrease the number of viable muscle stem cells, and this may result in a reduction in the number of cells able to regenerate the muscle as it recovers from inactivity and disuse (Favier 2008). Protein synthesis in muscle fibers takes place via activation of the Akt/mTOR pathway. As shown in Figure 1 (reviewed in Sandri 2008 and Gumucio 2013), growth hormone (GH) and insulin-like growth factor-1 (IGF-1) are potent inducers of muscle growth by directly activating the Akt/mTOR pathway and by promoting satellite cell proliferation (Vinciguerra 2010). Importantly, GH and IGF-1 can also directly inhibit the signaling activity of myostatin and other atrophy-inducing cytokines.

[figure not shown]

Figure 1. (A) Detailed overview of cellular signaling pathways that regulate muscle hypertrophy and atrophy. (B) Simplified overview demonstrating the role of GH, IGF-1 and myostatin in regulating muscle hypertrophy and atrophy.

Changes in Myostatin and Muscle Strength Over the Course of ACL Rehabilitation. To determine if circulating levels of myostatin changed over the course of ACL reconstruction and rehabilitation, we conducted a study of physically active patients who suffered an ACL tear (N=18, mean age 28±2 years; Mendias 2013). Patients were evaluated at 7 total visits, beginning one week prior to surgery, and seen at 6 post-operative visits until discharge at 26 weeks (Figure 2A). Blood was drawn at all study visits to measure circulating levels of myostatin and many other cytokines via ELISA or Luminex assay. Isokinetic knee extension strength (60°/second) was measured at the pre-op and last four post-op visits. All patients completed a supervised, accelerated rehabilitation protocol (Beynon 2005a). As shown in Figure 2B, there was a significant elevation of circulating myostatin levels at the first and second post-op visits. Knee extension strength was normalized to the uninvolved side at each study visit, and as shown in Figure 2C, at the time of surgery patients had reduced strength, and by the time of discharge patients still had a 30% strength deficit. These results are in agreement with results from a rat model of ACL tears (Delfino 2013), in which increases in the expression of intramuscular myostatin, atrogin-1 and MuRF-1 corresponded with muscle atrophy after ACL transection.

[figure not shown]

Figure 2. Changes in circulating myostatin and knee strength over the course of ACL reconstruction and rehabilitation. (A) Overview of study time points. Circulating (B) myostatin levels, and (C) knee isokinetic extension. Values are mean±SE, N=18. *, significantly different from pre-op value (one-way repeated measures ANOVA, Dunnett's post-hoc sorting).

GH to Counteract Muscle Atrophy and Weakness. GH has been well studied in several models of muscle atrophy and weakness. Although GH anecdotally has a reputation as a strong anabolic agent, several studies in humans have demonstrated that only at high doses does GH treatment induce appreciable muscle hypertrophy in otherwise healthy muscle (Chikani 2014). It is only when a

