Surveys and Recording of Patient-Reported Adverse Events. Patients will complete patient reported outcome measure (PROM) surveys at each visit to measure pain, function and physical performance, including (i) the Veterans Rand-12 (VR-12), to measure overall health-related quality of life (Selim 2009); (ii) the International Knee Documentation Committee (IKDC) survey, to evaluate knee-specific sports function (Anderson 2006), and (iii) the Knee injury and Osteoarthritis Outcome Score (KOOS), to evaluate knee-specific general and sports function (Roos 2003). Patients will also be asked to report adverse events associated with the use of GH, as described in the GH Self Reporting Symptom Form.

BioDex Strength Testing and Ultrasound Muscle Cross-Sectional Area Measurements. Whole muscle isometric and isokinetic strength measurements will be performed in a BioDex System 3 dynamometer as described (Mendias 2013). Maximum isometric force will be measured at 45° and 90° of knee flexion. Maximum isokinetic flexion and extension will be measured over a 90° arc at a velocity of 60°/second. All measures will be performed bilaterally, and the highest force from a series of five trials from each side will be used.

MRI Muscle Volume Measurements. Bilateral MRI scans will be performed at the pre-operative, third post-op and sixth post-op visit. Scans will be performed in a 3.0T magnet and will extend from hip to knee. The volume of the quadriceps and hamstring muscle groups will be determined using quantitative MRI analysis software.

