Outcome Measures. The overall objectives of the study are to evaluate if GH is safely tolerated in closely monitored patients undergoing ACL-R, and if so, to collect pilot and early efficacy data to determine if subsequent larger clinical trials are warranted. The primary outcome measure of the study is isokinetic knee extension strength at 26 weeks. Secondary outcome measures include isokinetic strength at other time points, MRI measurement of muscle size, PROMs, and circulating protein biomarkers (IGF-1, myostatin, MMP-3, and hyaluronic acid).

Sample Size and Statistical Analyses. We base the sample size for this study on maximum isokinetic knee extension values at the time of discharge from our previous study (Mendias 2013). To detect a 30% difference in isokinetic knee strength between the placebo and GH group, with a power of

80% and $\alpha=0.05$, requires $N=17$ per group. To account for any patient attrition, we will aim to recruit 7 additional patients for each group into the study for a total of $N=24$ per group or $N=48$ for the entire study. We will use a mixed-effects linear regression model (Zhang 2010) to look at the changes in individual parameters between the placebo and GH groups at multiple time points over the course of the study, as well as the associations between changes of multiple parameters. We will also perform interim data analysis to determine if there are significant differences in strength and other outcomes between groups.

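### The hypothesis claims return of full quadriceps strength by 6 months, but the planned analyses test only GH against placebo, and beating placebo does not show full strength

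*Combined protocol and SAP*

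**What the plan says.** The hypothesis, in Abstract and Hypothesis, has two clauses. Compared with placebo, six weeks of perioperative GH will prevent atrophy and weakness, and it will "cause the return of full quadriceps muscle strength by 6 months after surgery".

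Under Outcome Measures, "The primary outcome measure of the study is isokinetic knee extension strength at 26 weeks". The plan does not say whether this is absolute torque or a ratio to the other limb.

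Sample Size and Statistical Analyses sizes the trial "To detect a 30% difference in isokinetic knee strength between the placebo and GH group", with 80% power and alpha 0.05, at 17 per group, raised to 24 for attrition. The model looks at "changes in individual parameters between the placebo and GH groups at multiple time points over the course of the study" and at associations between parameters. The interim look has the same form: "We will also perform interim data analysis to determine if there are significant differences in strength and other outcomes between groups".

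On a reference for strength, the earlier cohort is described as follows: "Knee extension strength was normalized to the uninvolved side at each study visit". Its patients still had a 30% deficit at discharge. For this trial, the BioDex section says "All measures will be performed bilaterally, and the highest force from a series of five trials from each side will be used", but not how the uninvolved side enters the analysis.

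**The concern.** The second clause is a statement about the level reached in the GH arm, while every planned treatment comparison is a statement about a difference between arms. The plan gives no definition of full strength, no reference value and no margin. A significant difference from placebo could therefore be taken as support for the whole hypothesis when the GH arm still has a material deficit. This matters because the abstract links support for the hypothesis to faster safe return to play and to prevention of later osteoarthritis, and both depend on the level of strength regained.

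**Working it through.** **Inputs from the documents.** 17 per group before attrition and 24 after; power 80%; alpha 0.05; a 30% difference between arms (Sample Size and Statistical Analyses); a 30% deficit at discharge in the earlier cohort (Changes in Myostatin and Muscle Strength).

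**Assumptions.** The plan states neither the SD, nor the sidedness of the test, nor whether 30% is relative or in percentage points. I take a two-sided two-sample t-test, strength as a percentage of an uninvolved-limb reference, and placebo at 100 − 30 = 70%.

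**1. The plan's own figure.** The 17 per group cannot be reproduced forwards without an SD, so I solved backwards. With 17 per group, 80% power needs a standardised difference d = 0.991.
- Percentage points: SD = 30/0.991 = 30.3. The powered alternative is 70 + 30 = 100%.
- Relative to 70%: the difference is 0.30 × 70 = 21 points, so SD = 21/0.991 = 21.2. The powered alternative is 91%.

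The attrition arithmetic is correct: 17 + 7 = 24, and 2 × 24 = 48.

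**2. How far short of full can a significant result be?** The smallest observed difference with p<0.05 is t(0.975, 2n−2) × SD × √(2/n). For n=17 and SD 30.3 this is 2.037 × 30.3 × √(2/17) = 21.2 points.

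| SD | n per arm | Smallest significant difference | GH-arm mean if placebo is at 70% |
|---|---|---|---|
| 30.3 | 17 | 21.2 | about 91% |
| 30.3 | 24 | 17.6 | about 88% |
| 21.2 | 17 | 14.8 | about 85% |
| 21.2 | 24 | 12.3 | about 82% |

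**3. How well is the GH-arm level estimated?** The 95% CI half-width is t(0.975, n−1) × SD/√n. For n=17 and SD 30.3 this is 2.120 × 30.3/√17 = 15.6 points.

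| SD | n=17 | n=24 |
|---|---|---|
| 30.3 | ±15.6 | ±12.8 |
| 21.2 | ±10.9 | ±8.9 |

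An observed GH mean of exactly 100% would have a lower limit between 100 − 15.6 = 84.4% and 100 − 8.9 = 91.1%.

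**4. Could the trial support a claim of full return?** For illustration, assume a margin of 10 points and a true GH mean of 100%. By the normal approximation, power is Φ(10/(SD/√n) − 1.96).
- SD 30.3: about 28% at n=17 and 37% at n=24.
- SD 21.2: about 49% at n=17 and 64% at n=24.

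The margin is mine, since the documents give none. The SD of a ratio to a pre-treatment value may also differ from these back-solved values.

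**The case against.** The strongest reply is that the hypothesis is worded as a comparison with placebo, and that Outcome Measures limits the aim to tolerability and pilot efficacy data for deciding on larger trials. No sentence says that a positive between-arm test will be taken as proof of full recovery. Also, if the 30% is in percentage points, it equals the earlier cohort's 30% deficit, so the trial is powered at an alternative of full recovery. These points are fair and limit the severity, but they do not close the gap. Powering at an alternative of 100% does not test it: the test rejects equality with placebo, and step 2 shows that it can do so well below 100%. The second clause is still written as something the study will support or refute.

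A reader might go further and infer that the endpoint is a ratio to the uninvolved limb at the same visit, that the only available reference limb has itself been exposed to GH, and that the trial therefore loses substantial power. The documents do not support this.
- Same-visit normalisation describes the earlier cohort. This trial's endpoint is not said to be a ratio.
- Table 1 places bilateral strength testing at Preop 2, about two weeks before surgery. Dosing starts one week before surgery, so under Table 1 an unexposed value exists. Placebo patients' limbs are never exposed.
- The background says that GH gives appreciable growth in healthy muscle only at high doses, and dosing ends about 26 − 5 = 21 weeks before the endpoint. The distortion may be small, and the documents do not allow it to be sized.
- Any power loss rests on an assumed gain in the uninvolved limb. With an assumed 5% gain, a 100-versus-70 effect reads 100/1.05 − 70 = 25 points. At SD 30.3, power is then 65% to 67.5% at n=17 and 81% to 83% at n=24, depending on whether the GH-arm SD is held or scaled. With no gain, nothing is lost.

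What stands is narrower. A same-visit uninvolved-limb value is measured after randomisation and, in the active arm, after GH exposure, so it is the less suitable denominator if a ratio is used.

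**Conclusion.** The point holds as a mismatch between claim and analysis. The second clause of the hypothesis has no planned analysis, and a significant GH-placebo difference would not supply one. Under the stated assumptions, the trial could be positive at 17 per group with the GH arm at about 91% or 85% of the reference, and at 24 per group with about 88% or 82%. The level in the GH arm would be known only to within about 9 to 16 points. These figures depend on the back-solved SD, a two-sided t-test and placebo at 70%. The logical gap depends on none of them.

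The 17 per group is not shown to be wrong, and the between-arm primary comparison is sound for the first clause. This should be corrected before analysis, but it does not threaten the primary comparison.

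**What to change.** 1. Keep the between-arm comparison of the involved limb at 26 weeks as the primary analysis.
2. Add a secondary estimate: 26-week involved-limb peak torque as a percentage of the uninvolved-limb value measured before the first dose, reported by arm with 95% CI.
3. Define full strength in advance by naming the reference, when it is measured, and a justified margin below 100%. Claim full return only if the lower limit of the GH-arm CI exceeds that margin. Otherwise delete 'full' from the hypothesis and limit the conclusion to the difference from placebo.
4. Reconcile the timing of the baseline test. Table 1 puts it about two weeks before surgery, whereas Screening Visit and Initial Study Measurements puts initial measurements no more than one week before surgery, which is when dosing begins. The reference value must be confirmed as pre-treatment. Because tears may be up to six months old, it may already reflect some disuse, and the report should say so.
5. If any ratio to the uninvolved limb is reported, prefer the pre-treatment value to the same-visit one.

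The cost is protocol wording and one extra estimate from bilateral data already being collected, with no new visits or patients. The downside is a less favourable claim: at these sample sizes the trial may well be unable to support full return even if it occurs (step 4 of the working).

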Anabolic steroids are another well-studied class of compounds that can also protect muscle from disuse atrophy (Orr 2004). However, there are several systemic side-effects of a prolonged course of anabolic steroids such as elevated cholesterol and liver enzymes, alopecia and gonadal hypoplasia (Orr 2004). While these drugs have the potential to prevent muscle atrophy after inactivity, they also have a well-described negative impact on tendon and ligament healing (Freeman 1995, Inhofe 1995, Orr 2004, Marqueti 2006). In the case of a patient recovering from an ACL-R, anabolic steroids could possibly harm the proper healing and integration of the ACL graft. While GH has not directly been studied in the context of ACL healing, GH appears to be beneficial in promoting the healing and regeneration of soft tissue injuries (Vestergaard 2012, Boesen 2014). We therefore anticipate GH to at the minimum not impair, but also potentially help to accelerate the repair and reintegration of the ACL graft.

[figure not shown]

Figure 2. Changes in cross-sectional area (CSA) (muscle and patellar tendon) and maximal muscle strength during 2 weeks of immobilisation and 6 weeks of re-training in young males (n = 20) with either recombinant human growth hormone (rhGH) (n = 10) or placebo (n = 10)
A, CSA of the quadriceps muscle; time effect ($P < 0.01$) and group interaction ($P = 0.09$). B, CSA of the patellar tendon; time effect ($P < 0.01$) and group interaction ($P < 0.05$). C, maximal isometric muscle strength; time effect ($P < 0.01$) and group interaction ($P = 0.09$). *Time effect, $P < 0.05$, compared with baseline (both groups). §Time effect, $P < 0.05$, compared with Post immob (both groups). \$Time effect, $P < 0.05$, baseline/Post immob. vs. 2 weeks of re-training (GH). Data are means \pm SEM.

Figure 3. From Boesen 2013.

Study Design and Experimental Methods

Overall Study Design. This is a prospective, double-blind placebo-controlled basic science-focused study to evaluate the ability of GH to prevent atrophy in patients undergoing surgical reconstruction of a torn ACL. The time points of the study were chosen based on our previous work in studies of ACL-R (Mendias 2013), and because they represent important hallmarks in the rehabilitation of patients undergoing rehab for an ACL-R (Beynon 2005a). With the exception of growth hormone or placebo administration, blood draws, additional MRI scans, strength measures and surveys, the study does not

[figure not shown]

Figure 4. Overview of the study time points.

deviate from the standard of care typically provided to patients undergoing ACL-R. An overview of the timeline of study visits is presented in Figure 4 and Table 1. This study is registered on Clinicaltrials.gov (NCT02420353) and was granted an IND exemption by the FDA (IND 123189).

| Study Visit | Measures Performed |
|-------------------------------------|---|
| 1. Preop 1 (~4 wk prior to surgery) | History/vitals, blood draw, vital signs |
| 2. Preop 2 (~2 wk prior to surgery) | Surveys, BioDex (isometric, isokinetic), MRI, medication instruction, vital signs |
| 3. Postop 1 (~1 wk after surgery) | Surveys, blood draw, medication check, vital signs |
| 4. Postop 2 (~2 wk after surgery) | Surveys, blood draw, medication check, vital signs |
| 5. Postop 3 (~5 wk after surgery) | Surveys, BioDex (isometric, isokinetic), MRI, blood draw, medication check, vital signs |
| 6. Postop 4 (~12 wk after surgery) | Surveys, BioDex (isometric, isokinetic, balance), blood draw, vital signs |
| 7. Postop 5 (~18 wk after surgery) | Surveys, BioDex (isometric, isokinetic, balance), blood draw, vital signs |
| 8. Postop 6 (~26 wk after surgery) | Surveys, BioDex (isometric, isokinetic, balance), MRI, blood draw, vital signs, patient discharged from the study |

Table 1. Timeline of study visits and measures performed in this proposal.

Patient Selection and Recruitment. This study is based on an already approved protocol by the University of Michigan Medical School Institutional Review Board (study # HUM00038126). All patients will provide informed consent prior to participating in the study.

Inclusion Criteria:

1. Males between the ages of 18 and 35
2. Have acute unilateral complete ACL tears with or without bucket handle medial meniscus tears that occurred within the past 6 months
3. Consent to undergo an ACL reconstruction by [name] using a patellar tendon or hamstring autograft
4. Will be performing supervised post-operative rehabilitation at UMHS MedSport at Dominos Farms ([name])

Exclusion Criteria:

1. Patients who are undergoing a revision ACL reconstruction
2. Had a previous injury to the involved knee
3. Have an allergy to recombinant GH
4. Have a BMI < 20 or > 35

5. Have a growth disorder of bones or connective tissue, type 1 diabetes mellitus, type 2 diabetes mellitus, or who have a history of carpal tunnel syndrome, trigger finger, myopathy, cancer, endocrine disorder, hypertension or rheumatologic disorder.
6. Systolic blood pressure >140mm Hg or diastolic blood pressure >90mm Hg, or with resting heart rate >110 BPM or <40 BPM at screening.
7. Additionally, because GH is currently listed as a banned substance by the World Anti-Doping Agency (WADA), National Collegiate Athletics Association (NCAA) and most professional sports agencies, we will exclude patients who are current collegiate, professional or elite athletes.

We will recruit up to 48 total patients (24 placebo control, 24 GH), recruited at a rate up to 3 to 6 patients per month. Interim data analysis will be performed, and actual sample sizes may be lower based on safety assessments and the effect of GH on strength.

We will exclude women from this study due to the consequences GH can have on reproductive cycles, and because GH can decrease the efficacy of birth control medications. Additionally, GH could have detrimental effects on a developing fetus. For these reasons, we are excluding women from participation in this study.

Screening Visit and Initial Study Measurements. Patients who consent to surgery and are interested in participating in the study will be seen at a screening visit. The screening visit will typically occur after a normal clinic visit, but may be scheduled at the convenience of the patient. The vital signs of patients will be measured, the history will be recorded, and patients will be asked to report to an M-Labs testing location for fasting blood work within the next 5 days. The labwork includes complete blood count with platelet differential, metabolic panel (glucose, urea nitrogen, creatinine, sodium, potassium, chloride, CO₂, calcium, total protein, albumin, total bilirubin, AST, ALT and alkaline phosphatase), lipid panel (total cholesterol, triglycerides, HDL cholesterol, LDL cholesterol), hemoglobin A_{1c}, high sensitivity CRP, creatine kinase, and IGF-1 (as described below). Patients who have normal values based upon M-Labs guidelines will be permitted to enroll in the study. Patients with minor deviations (typically less than 10%) from normal values may be allowed to participate based on consultation with [name] and [name]. Patients who do not pass screening will be provided with \$25 compensation.

After assessing vitals and lab work, patients will be scheduled for an MRI, and for an appointment at MedSport where strength and stability measurements, completion of surveys and instruction on medication use will be performed. All screening and initial study measurements will be performed no more than one week before surgery.

Surgical Reconstruction and Postoperative Rehabilitation. Patients will have a thorough history and physical examination performed by [name]. Examination under anesthesia will be performed to confirm functional instability and document the extent of meniscus tear. Surgical reconstruction of the ACL will be performed using autologous graft from the ipsilateral knee, and a partial meniscectomy or meniscal repair will be performed to repair the meniscal defect. A single-bundle, anatomic “center-center” ACL-R will be performed (Bedi 2009). Patients will follow a standard, supervised accelerated ACL rehabilitation protocol postoperatively (modified from Kim 2003, Beynon 2005a). Rehabilitation begins with quad sets, straight leg raises, ankle pumps, heel slides, and partial weight bearing up to 25% in the first week. These exercises continue into the second and third weeks, with the addition of electrical stimulation for muscle reeducation, leg press, core and hip exercises, stationary biking, and progression to 50% weight bearing. From weeks 4 to 12, additional closed chain resistance exercises are added and patients progress to full weight bearing and open chain exercises. From weeks 12 to 20,

exercises increase in load and complexity, and patients progress to a jogging program. Agility and plyometric training begin at week 20, and continue in complexity and intensity based on passing functional tests demonstrating appropriate gait and motor control.

Surveys and Recording of Patient-Reported Adverse Events. Patients will complete patient reported outcome measure (PROM) surveys at each visit to measure pain, function and physical performance, including (i) the Veterans Rand-12 (VR-12), to measure overall health-related quality of life (Selim 2009); (ii) the International Knee Documentation Committee (IKDC) survey, to evaluate knee-specific sports function (Anderson 2006), and (iii) the Knee injury and Osteoarthritis Outcome Score (KOOS), to evaluate knee-specific general and sports function (Roos 2003). Patients will also be asked to report adverse events associated with the use of GH, as described in the GH Self Reporting Symptom Form.

BioDex Strength Testing and Ultrasound Muscle Cross-Sectional Area Measurements. Whole muscle isometric and isokinetic strength measurements will be performed in a BioDex System 3 dynamometer as described (Mendias 2013). Maximum isometric force will be measured at 45° and 90° of knee flexion. Maximum isokinetic flexion and extension will be measured over a 90° arc at a velocity of 60°/second. All measures will be performed bilaterally, and the highest force from a series of five trials from each side will be used.

MRI Muscle Volume Measurements. Bilateral MRI scans will be performed at the pre-operative, third post-op and sixth post-op visit. Scans will be performed in a 3.0T magnet and will extend from hip to knee. The volume of the quadriceps and hamstring muscle groups will be determined using quantitative MRI analysis software.

Blood Draw. Approximately 6-8mL of blood will be drawn from an antecubital vein and collected into either a K₂-EDTA tube for plasma preparation or a clot activator tube for serum preparation. A portion of the plasma or serum will be used for clinical labs performed by UMHS M-Labs and a portion will be stored at -80°C for measurement of different proteins in [name] lab. The tests performed by M-Labs include a complete blood count with platelet differential, metabolic panel (glucose, urea nitrogen, creatinine, sodium, potassium, chloride, CO₂, calcium, total protein, albumin, total bilirubin, AST, ALT and alkaline phosphatase), lipid panel (total cholesterol, triglycerides, HDL cholesterol, LDL cholesterol), hemoglobin A_{1c}, high sensitivity CRP, creatine kinase, and IGF-1. For measurements performed in [name] lab, the levels of myostatin (as a marker of muscle atrophy), MMP-3 (as a marker of cartilage catabolism), and hyaluronic acid (as a marker of cartilage catabolism) will be measured in duplicate using ELISAs as described (Mendias 2013).

Vital Signs. Patients' heart rate, temperature, blood pressure and respiratory rate will be recorded at each visit.

Wallet Card. Patients will be provided with a laminated card to carry in their wallet or purse in case of emergencies. The card will state that the patient is currently enrolled in a clinical trial evaluating GH, that they are taking either GH or placebo and the contact information for [name], [name], [name] and the study research coordinator.

Administration of GH or Placebo. The UMHS Pharmacy IDS service will be used to assist with storing, preparing and dispensing drug. We will use Humatrope (somatropin of rDNA origin, Eli Lilly) as the test drug, and sterile bacteriostatic saline with no active hormone will serve as the control. We will use sterile insulin syringes to deliver drug or placebo subcutaneously. Patients will be provided with the manufacturer's instructions for the use of Humatrope, all supplies (needles, alcohol swabs, cartridges containing GH or placebo, disposal container) and will also receive personalized instruction on how to

prepare and deliver GH using a mock system by study personnel. Patients will be instructed to rotate injection sites to minimize discomfort.

GH dose will be calculated by nomogram estimation of body surface area, and will be administered via subcutaneous injection in the abdominal area twice per day (BID) at a dose of 0.5mg GH per body surface area (BSA) in m² (0.5mg/m²). We will use the DuBois equation to predict BSA [$BSA(m^2) = 0.007184 \times Height(cm)^{0.725} \times Mass(kg)^{0.425}$], which is a commonly accepted equation in clinical medicine. This dose has previously been shown by [name] to effectively increase systemic IGF-1 levels with minimal side effects (Surya 2009). Patients will begin GH treatment one week prior to surgery and will continue through 5 weeks after surgery. On the day of surgery, patients will not take GH, but otherwise patients will take GH every day over this 6 week period. Patients will be asked to keep a log detailing their injections, and will be asked to return all used and unused supplies for inventory.

While GH is currently not indicated for orthopaedic muscle atrophy, GH does have an FDA indicated use for the treatment of HIV-associated muscle atrophy and wasting. Although the FDA approved label of Humatrope does not specifically indicate an approved use for treating HIV-associated muscle atrophy and wasting, there is a form of somatotropin, Serostim, that is FDA approved to be marketed specifically for the of HIV-associated muscle wasting. Other than slight differences in preservatives, Humatrope and Serostim are identical forms of somatotropin. The FDA approved dose of somatotropin for the treatment of HIV-associated muscle wasting and cachexia is 0.1mg/kg subcutaneously daily, up to 6mg total per day. Several clinical trials have shown these doses to be generally safe, even in immune compromised HIV+ individuals, as well as effective at preventing cachexia, although there is an attenuation of protection against atrophy after 12 weeks (reviewed in Gelato 2007). Based on an individual who has a BSA of 2.25m² (188cm tall and 100kg in mass), which is our estimate of the high end of subjects in this study, the dose of somatotropin would not differ substantially from levels used to prevent muscle atrophy in patients with atrophy and cachexia caused by HIV infection. There are likely similar mechanisms behind ACL tear-related and HIV-related muscle atrophy, as an elevation in myostatin has been identified in both groups of symptomatic patients (Gonzales-Cadavid 1998, Mendias 2013), and GH can downregulate myostatin expression both directly and indirectly through the activity of IGF-1 (Liu 2003, Morissette 2009). The total dose of GH is also similar to that of Boesen (2013), who used a scheme of 33-50µg/kg/day (for a 100kg subject, this would be approximately 3.3-5mg/day) in otherwise young, healthy subjects who underwent lower limb cast immobilization to simulate muscle atrophy. In this study, subjects in the treatment group (N=10) received an initial dose of 33µg/kg/day for one week followed by 50µg/kg/day for 7 weeks, while the control group (N=10) received placebo injections. Of the 10 subjects who received GH, only 3 reported adverse events (carpal tunnel syndrome, and one of these also reported trigger finger) at the 50µg/kg/day dose. When the dose was adjusted down to 33µg/kg/day the symptoms resolved and the dose was then increased back to a tolerable dose that approached 50µg/kg/day. As the dose of GH used in the proposed study is less than that of Bosen (2013), and symptoms only appeared at 50µg/kg/day, we anticipate that the dose of GH in the current study will not result in side effects in our study population.
